9.6 Data Management

Data will be collected and entered in eCRFs within a validated EDC system that is compliant with all regulatory requirements. The web-based EDC system aims to serve as a transparent tool to collect and manage data and track study progress at the patient level. Data in the EDC system are kept in a central location.

Site staff will be trained by the sponsor representative or delegate to perform the chart abstraction, including data entry and how to retrieve and respond to data queries in the EDC system. It is assumed that participating sites will be able to complete data entry into the eCRFs via the EDC system.

The sponsor representative or delegate will supervise and perform site management and monitoring as described in the study-specific monitoring plan. All participating sites will only have access to view and enter the data for their own patients. Only data required by the protocol for the purposes of the study should be collected.

The patient's routine clinical care treating physician has the ultimate responsibility for the collection and reporting of all clinical, safety, and treatment data entered into the eCRF and ensuring any other data collection forms (source documents) are accurate, authentic/original, attributable, complete, consistent, legible, timely, enduring, and available when required. The eCRFs must be electronically signed by the treating physician or by an authorized staff member to attest that the data contained on the eCRFs are true, complete, accurate and verifiable to source records. The argenx representative or delegate will inform sites when it is time for eCRF sign-off to occur.

Each site will maintain a Patient Identification list linking the patient to the Patient Identification within the EDC. Only the treating physician and/or authorised personnel will be able to identify the patient based on the Patient Identification list, which will be held only at the site.

The Investigator must permit study-related monitoring, audits, Institutional Review Board (IRB)/Independent Ethics Committee (IEC) review, and regulatory agency inspections and provide direct access to source data documents.

9.7 Data Analysis

The Full Population will be all patients enrolled.

The Safety Population will include all patients enrolled who have taken at least one dose of efgartigimod for the efgartigimod cohort and all patients enrolled into the non-efgartigimod cohort. All analysis will be based on the Safety Population.

Unless otherwise specified, categorical endpoints will be summarised using counts and percent; continuous endpoints will be summarised using mean, standard deviation, median, minimum and maximum values. Statistical analysis will be mainly descriptive in nature using metrics such as

incidence proportion, exposure-adjusted incidence rate, confidence intervals, etc. Details of the analysis plan will be specified in the Statistical Analysis Plan (SAP).

Primary objective

Descriptive statistics will be used to summarise the long-term safety of efgartigimod, including the occurrence of events of serious infections, in gMG patients treated with efgartigimod compared to gMG patients not exposed to efgartigimod. The number and percentage of patients with AEs/SAEs will be presented. The rate per person-year exposure with a 95% CI will be constructed using asymptomatic normal approximation.

Although no formal hypothesis will be tested in the study, statistical models will be used to test the difference of incidence between treatment cohorts (efgartigimod vs. comparator). Two base models which are widely used to model incidence proportion and incidence rate adjusted by potential confounders will be used:

1. To model incidence proportions, a logistic regression model will be used including patients with event vs. patients without event as the response variable and treatment group and country as covariates.
2. To account for varied follow-up time, a Cox regression model will be used with time to the first occurrence of event for each patient as the response variable, treatment group and country as covariates .

Countries with small sample sizes will be combined with other countries based on the geographic locations. Other covariates may be added to the above base models as described below.

Balance of the baseline measures, including age, MG-ADL score and region matched at enrollment and other demographic and disease characteristics, will be assessed. The imbalanced measures which are considered to be potential confounders based on clinical judgement will be added to the above base models as covariates. If a large number of imbalanced potential confounders are identified after the enrollment is complete, a propensity score method will be applied instead. More details will be given in the SAP.

Subgroup analyses will be performed using descriptive statistics on the subset of patients who remained on efgartigimod throughout the duration of the PASS. In addition, subgroup analyses of treatment cycle per year or administration per year (four administrations in one cycle if not interrupted), subgroup analyses of time since the last administration of efgartigimod prior to the event occurrence in intervals of every 4 weeks will be performed, and subgroup analysis of patients using efgartigimod as add-on or single treatment will be performed if sample size allows. Since one patient may have multiple same events with different time to the last administration, one patient may be assigned to multiple time intervals.

Events of Interest

Statistical analysis of malignancy and other events of interest will follow the same method as those for serious infections

Exploratory objectives

Descriptive statistics will be used to summarise the long-term safety of efgartigimod for specific subgroups. The number and percentage of patients with AEs/SAEs will be presented. The rate per person-year exposure with a 95% CI will be constructed using asymptomatic normal approximation. This will be done for the following subgroups:

- immunocompromised patients and immunocompetent patients.
- patients treated with monoclonal antibodies and patients not treated with monoclonal antibodies.
- patients who have received live/attenuated vaccine and patients who have not received live/attenuated vaccine.
- patients with moderate to severe renal impairment and patients with normal renal function or mild renal impairment.

Missing values

No imputation will be applied to occurrence of serious infection, malignancy or other safety events.

For baseline measures which are potential confounders, descriptive analysis and balance assessment will be based on observed cases. The missing values of imbalanced potential confounders used as covariates in the statistical modelling will be imputed using the mean from non-missing values for continuous variables or a missing category for categorical variables.

Coding

Concomitant medications will be coded according to the World Health Organization (WHO) -Drug Dictionary. Patients with concomitant medications will be summarised by Anatomical Therapeutic Chemical (ATC) class and Preferred Term (PT) using descriptive statistics described above using the Full Population.

All AEs will be coded by PT and associated primary SOC using the MedDRA dictionary. The electronic case report AE form collects the verbatim term for MedDRA coding. AEs will be presented by SOC and PT using descriptive statistics described above using the Safety Population.

Details of the data analysis will be outlined in the SAP.

Representativeness of the study population

The characteristics of the enrolled population will be analysed after study enrolment is completed; baseline characteristics will be compared to the characteristics of the gMG population from real world studies in the literature to identify any potential differences. Details on this comparison will be included in the SAP.

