8. RESEARCH QUESTION AND OBJECTIVES

A non-interventional Post-Authorization Safety Study (PASS) in a post-marketing setting comparing cohorts of patients with gMG treated with efgartigimod to those treated with other MG medication for 10 years, in order to estimate incidence rates of serious infection and other safety events.

Primary Objective

- To evaluate the overall long-term safety of efgartigimod including the occurrence of serious infections in gMG patients treated with efgartigimod compared to gMG patients not exposed to efgartigimod.

Exploratory Objectives

- To evaluate the safety of efgartigimod in immunocompromised patients
- To evaluate the safety of efgartigimod administered to patients treated with monoclonal antibodies
- To evaluate the safety of efgartigimod in patients receiving live/attenuated vaccine
- To evaluate the safety of efgartigimod in patients with moderate to severe renal impairment

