9. RESEARCH METHODS

9.1 Study Design

This is a non-interventional, prospective, post authorisation safety study.

Patients with gMG who are expected to start treatment with efgartigimod at enrolment or are within their first cycle of efgartigimod at enrolment will be eligible to enrol into the efgartigimod cohort. Patients with gMG who have not been exposed to efgartigimod and for whom it is not planned to start treatment with efgartigimod at enrolment will be eligible to enrol into the non-efgartigimod cohort. It is anticipated that 340 patients will be enrolled in each cohort.

Patients will be treated and observed according to normal clinical practice. Participation in this study does not limit the physicians` clinical decision making as to the most appropriate treatment for the patient during the course of the study. No visits or investigations outside of normal clinical practice will be required. The enrolled patients will be followed prospectively until end of study participation, loss to follow up, consent withdrawal, or death, whichever comes first. All adverse events (AEs) will be collected throughout the duration of the study.

Enrolment of patients will be over a 5-year period. The follow up of patients will continue for 5 years from the time the last patient has been enrolled. Patients will be followed regardless of whether they continue or discontinue efgartigimod. Assuming a 5-year enrolment period this will allow for a maximum of 10 years of follow-up and a minimum of 5 years. A patient will be considered to be an efgartigimod exposed patient if he/she has received at least one dose of efgartigimod.

In order to minimise heterogeneity between the two cohorts, patients in the efgartigimod cohort will be matched at enrollment with a patient in the non-efgartigimod cohort for the following criteria:

- Age (\pm 5 years)
- Myasthenia Gravis -Activities of Daily Living (MG-ADL) score (0-5, 5-9, and >9) ([Wolfe, 1999](#))
- Region (within EU and within US)

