9.2.2 Study Procedures

Patient care will follow the normal treatment practices in the respective country and at the specific site. All patients in the study will receive care according to usual clinical practice, and clinical care will not be mandated by the protocol. No additional visits or investigations will be performed beyond usual clinical practice. The choice of ongoing medical treatment for the duration of the study will be made independently by the physician in the regular course of practice and will not be influenced by participation in this study.

Patient enrolment will be over a 5-year period. The follow-up of patients will continue for 5-years from the time the last patient has been enrolled. Patients will be followed regardless of whether they continue or discontinue efgartigimod. Thus, patients enrolled at the beginning of the study may be followed for a maximum period of 10-years.

Efgartigimod or any other treatment will not be provided by or paid for by argenx. Assessments are as per standard of care and will not be provided by or paid for by argenx.

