gMG treatments at or following enrollment (excluding efgartigimod)	
 Drug name, dose, start and stop dates 
 Acetylcholinesterase inhibitors Corticosteroids Other Immunosuppressants (specify) Monoclonal antibodies (specify) Plasmapheresis/plasma exchange acute Plasmapheresis/plasma exchange chronic IVIg therapy acute IVIg therapy chronic Other 	✓	✓

Category	Variables	Baseline	Follow up
Efgartigimod treatment	
 • Date of administration • Reason for interruption during cycle of treatment • Reason for permanent discontinuation whilst on study 	✓	✓
Other comedications at or following enrollment for conditions other than gMG	
 • Drug name, start and stop dates • Indication 	✓	✓
Live/attenuated vaccinations 2 months prior to enrollment to 2 months after last Vyvgart dose	
 • Live/attenuated vaccine 
 ○ Vaccine ○ Date 	✓	✓
Adverse Events (AEs)/Serious Adverse Events (SAEs)	
 • AEs, SAEs 		✓
Events of interest	See Table 2		✓

*All variables will be collected ONLY if available as part of routine clinical practice

A patient will be considered to be an efgartigimod exposed patient if he/she has received at least one dose of efgartigimod.

Additionally, taking into account the variable follow up time and time interval between cycles, the following will be measured for efgartigimod:

- Number of administrations per year
- Total duration of the exposure
- Total number of administrations

The exposure time window of efgartigimod is 56 days +/-3 days after the last dose.

Events of interest in this study will be pre-specified as per [Table 2](#) below.

Table 2: Pre-specified events of interest

Event of interest	Definition	Measurement
Serious infection	Any serious adverse event coded to the Medical Dictionary for Regulatory Activities (MedDRA) System Organ Class (SOC) of Infection and Infestation. See Section 11 for definition of Serious.	Proportion of patients who report serious infections during the course of the study in the efgartigimod treated cohort compared to the non-efgartigimod cohort. Incidence rate of serious infections per patient-years exposed in the efgartigimod treated cohort compared to the non-efgartigimod cohort.

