The study design includes an efgartigimod cohort and a comparator cohort of non-efgartigimod treated patients. The duration of the study is a maximum of 10 years (5 years of enrolment and 5 years of follow up). Over this time period, standard of care for the treatment of gMG is likely to evolve with the introduction of new medicinal products such as ultomiris (recently approved) and rozanolixizumab and zilucoplan (currently under review with an approval expected by end of 2023) and the potential for patients to switch treatments during this time. The comparator group, and indeed the efgartigimod group, will therefore be heterogenous in terms of treatments, thus limiting the interpretability of the results.

Furthermore, in countries where efgartigimod is marketed, it is likely that the efgartigimod cohort and the comparator cohort will differ in terms of disease severity with the more severe patients receiving efgartigimod. Thus, there will be an inherent selection bias. This could be solved by recruiting the comparator patients from countries where efgartigimod is not marketed. However, this will introduce further biases in terms of differing standards of care.

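### Comparator follow-up is not ended or split when a non-efgartigimod patient starts efgartigimod, so later events and time count as non-efgartigimod

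*Protocol*

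**What the plan says.** The primary objective (protocol, section 8) sets efgartigimod-treated patients against the comparator in these words: "compared to gMG patients not exposed to efgartigimod". Entry to the comparator cohort (section 9.1) is judged once. The patient has had no efgartigimod and is someone "for whom it is not planned to start treatment with efgartigimod at enrolment". After that, treatment is free: "The choice of ongoing medical treatment for the duration of the study will be made independently by the physician" (section 9.2.2). Patients are "followed prospectively until end of study participation, loss to follow up, consent withdrawal, or death, whichever comes first" (section 9.1), and a first efgartigimod dose is not on that list. Section 9.9 expects "the potential for patients to switch treatments during this time" and treats it as a limit on interpretation, with no analysis rule attached.

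Section 9.7 takes into the Safety Population "all patients enrolled into the non-efgartigimod cohort. All analysis will be based on the Safety Population". The logistic and Cox base models each contain treatment group and country, and treatment group is not described as varying over time.

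Two further sentences concern exposure. Sections 9.1 and 9.3 both state: "A patient will be considered to be an efgartigimod exposed patient if he/she has received at least one dose of efgartigimod". Section 9.3 adds: "The exposure time window of efgartigimod is 56 days +/-3 days after the last dose". Neither is tied to the between-cohort models. The ENCePP checklist (Annex 2, section 5) answers No on exposure definition and time windows and refers to the SAP.

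**The concern.** Take a comparator patient who starts efgartigimod in year 2 and has a serious infection in year 4 while still being treated. Under section 9.7 that infection, and all time from year 2 onwards, belongs to the non-efgartigimod side. The objective is worded by exposure, and after year 2 this patient is exposed.

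If efgartigimod raises the risk of serious infection or malignancy, such patients carry part of the excess into the comparator, and the contrast shrinks. For a safety study that is the unfavourable direction, because a real harm becomes harder to see.

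The one-dose sentence offers an analyst another route: count switchers as exposed from enrolment. The event-free time before the first dose would then be credited to efgartigimod, which is immortal-time bias. The protocol does not instruct this, but it does not rule it out.

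**Working it through.** **Inputs from the protocol (section 9.5 and Table 4).** Comparator risk 20%, efgartigimod risk 31%, 270 per arm, two-sided 0.05, normal approximation, stated power 84%. Follow-up 5 to 10 years.

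**Assumptions, not in the documents.** Constant hazards. Follow-up time T uniform on 5 to 10 years. A share c of comparators (10%, 20%, 30%) is due to switch, at a time uniform over follow-up. The treated hazard applies from the switch onwards.

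**Step 1: the plan's own figure.** SE = √[(0.20×0.80 + 0.31×0.69)/270] = 0.0370. Power = Φ(0.11/0.0370 − 1.96) = 84.0% with unpooled variance (83.7% with pooled variance under the null). Table 4's 84% is reproduced. It presupposes a comparator free of efgartigimod exposure.

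**Step 2: hazards.** Mean risk over T is 1 − (e^(−5λ) − e^(−10λ))/(5λ). Setting this to 0.20 and 0.31 gives λ0 = 0.0299 and λ1 = 0.0498 per year, a ratio of 1.67.

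**Step 3: risk of a switcher.** Averaging 1 − exp(−λ0·u − λ1·(T − u)) over u uniform on (0, T) and over T gives 25.6%. A hand check with half of follow-up after the switch agrees: 1 − exp[−½(0.223 + 0.371)] = 25.7%, where 0.223 = −ln 0.80 and 0.371 = −ln 0.69.

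**Step 4: switchers kept in the comparator.** Comparator risk = (1 − c)×20% + c×25.6%. Power is unpooled.

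| c | Comparator risk | Difference (points) | Power, n = 270 | Power, n = 330 |
|---|---|---|---|---|
| 0 | 20.0% | 11.0 | 84% | 90% |
| 10% | 20.6% | 10.4 | 80% | 87% |
| 20% | 21.1% | 9.9 | 75% | 83% |
| 30% | 21.7% | 9.3 | 69% | 78% |

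Worked for c = 20% and n = 270: 0.8×20% + 0.2×25.6% = 21.1%; SE = 0.0375; Φ(0.0987/0.0375 − 1.96) = 75%. In the extreme case where every switch comes right after enrolment, power at n = 270 is about 75%, 64% and 52%.

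**Step 5: the three ways of attributing time.** Simulated rate ratios with the same hazards. Only patients still event-free switch, so about 9%, 18% and 27% of comparators actually do.

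| c | True ratio | Enrolment cohort | Exposed from enrolment | Split at first dose |
|---|---|---|---|---|
| 10% | 1.67 | 1.62 | 1.52 | 1.67 |
| 20% | 1.67 | 1.57 | 1.36 | 1.67 |
| 30% | 1.67 | 1.53 | 1.22 | 1.67 |
| 10% | 1.00 | 1.00 | 0.91 | 1.00 |
| 20% | 1.00 | 1.00 | 0.82 | 1.00 |
| 30% | 1.00 | 1.00 | 0.74 | 1.00 |

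Splitting at the first dose recovers the true ratio here because switching does not depend on prognosis in this simulation. In a separate check with no true effect, where switching took no account of whether the event had already happened, the exposed-from-enrolment ratio stayed near 1.

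**The case against.** **Exposure handling is left to the SAP.** The checklist says so, and start-stop coding is ordinary SAP content. This would be decisive if the protocol were silent. It is not: section 9.7 already fixes the comparator's membership and a treatment group that does not vary. A SAP that splits time would be supplying a rule those sentences do not contain.

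**The protocol does not say in words that switchers stay in the comparator.** True. It follows from the analysis set, the fixed group and the absence of any censoring event. Section 9.7 defines who is analysed, while the 56-day window and the rates per exposed patient-year leave a person-time reading open. That reading would largely solve the problem, but nothing connects it to the between-cohort models.

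**A reader might infer that sections 9.1 and 9.3 flatly contradict section 9.7.** The documents do not support that. The efgartigimod cohort admits patients merely expected to start, so the one-dose sentence can be read as the minimum exposure for that cohort, as in section 9.7. No section moves pre-dose time into exposed time. What stands is that the sentence is not limited by cohort or date.

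**Analysis by enrolment cohort is legitimate.** It preserves the enrolment matching and suits long-latency malignancy. Section 9.9 expects more severe patients to receive efgartigimod, so censoring at the switch may be informative. Both points stand and shape the fix.

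**Power is secondary.** Section 9.5 sizes the study on precision and calls the analysis descriptive and exploratory. That is fair: the shrunken contrast matters more than the lost power. At 330 per arm, 20% switching still leaves about 83%.

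**Conclusion.** The point holds as a gap in how comparator time is attributed. As written, events and person-time after a first efgartigimod dose count as non-efgartigimod, and any true excess risk is pulled towards no difference. Under the assumed 10% to 30% switching, the loss is 0.6 to 1.7 of the 11 points, and power at 270 per arm falls by about 4 to 15 percentage points. The switching rate and the permanent treated hazard after a switch are assumptions; with the 56-day window the true dilution could be smaller.

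Two stronger inferences should be resisted. One is that the comparison is biased whichever reading is used. The enrolment-cohort reading is undistorted without switching or without a true effect, and the exposed-from-enrolment bias arises when switching depends on being event-free. The other is that the two readings err in opposite directions. Where efgartigimod raises risk, both make it look safer (at 20% switching, 1.67 becomes about 1.57 and 1.36).

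**What to change.** Reconcile sections 9.1, 9.3 and 9.7 as follows:

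- **Cox model and person-time rates.** End a comparator's non-efgartigimod time at the first efgartigimod dose and count later time as exposed. State how the 56-day window applies to that time.
- **Logistic model and incidence proportions.** These cannot split person-time. Either count only comparator events before the first dose, or label the result an enrolment-cohort analysis.
- **Enrolment-cohort analysis.** Keep it as a sensitivity analysis; it is also useful for long-latency malignancy.
- **One-dose sentence.** State that it does not reclassify follow-up before the first dose.
- **Informative switching.** Add a sensitivity analysis with time-updated covariates or censoring weights.

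The cost is wording in the protocol and SAP, and start-stop programming. Table 1 already collects administration dates, so no new data are needed. The downside is the risk of informative switching, which the last analysis addresses only as far as the recorded covariates allow. The rule should be set before switching is observed, so that it is not chosen after the fact.

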In the EU RMP, use of efgartigimod in immunocompromised patients, in patients with moderate to severe renal impairment, in patients taking concomitant monoclonal antibodies and in patients receiving

live/attenuated vaccines is considered to be missing information as efgartigimod has not been studied in these patient populations. This post authorisation safety study will include these patient populations according to normal clinical practice. If these patients are enrolled into the study, the safety of efgartigimod will be assessed in these patient populations.

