9.5 Study Size

A sample size of 340 patients in each of the two cohorts is proposed (680 patients in total). Recruitment will be over a 5 year period and patients will be followed for 5 years from the time the last patient is enrolled. Thus maximum follow up will be 10 years.

The estimated prevalence rate for MG is 77.7 per million persons (range 15-179) and the estimated incidence rate is 5.3 per million person-years (range 1.7–21.3).

Myasthenia gravis occurs in both genders, at all ages, and in all races. However, for sample size calculations it is proposed to use the reported serious infection prevalence in MG patients.

Statistical analysis in this study will be descriptive and exploratory, and not aimed to confirm or reject predefined hypotheses.

Sample size calculation is driven by the precision of the estimated incidence proportion of serious infection assuming similar incidence proportion to the background.

In a population-based cohort study of 3823 MG patients ([Kassardjian 2020](#)) followed for a mean of 5.4 (Standard Deviation [SD]=3.8) years, 33.4% of patients experienced a serious infection which included both emergency department visits and hospitalisation with primary diagnosis of infection. In a retrospective chart review of 358 MG patients ([Prior 2018](#)) over a 10-year period, 19% of patients experienced infection. In the argenx-sponsored ADAPT+ study final analysis with 145 efgartigimod patients followed for a mean of 1.7 years (SD=0.7), 6.2% of patients experienced at least one serious infection (serious adverse event with SOC term "Infections and Infestations").

For the current study, serious infection incidence proportion is assumed to be 20% considering varied follow-up time and definitions of serious infection in the literature and argenx-sponsored trial.

The sample size needed to achieve a 5% precision (half-width) is presented in Table 3 below with the following assumptions:

- An incidence proportion of 20% for serious infections among patients receiving efgartigimod.
- Two-sided 95% exact binomial confidence limits based on the Clopper-Pearson method.

Table 3: Precision calculations for different incidence proportions

Number of Patients	Expected Incidence Proportion	Expected Number of Patients with Event*	Lower Limit of 95% Confidence Interval (CI) of Observed Incidence Proportion	Upper Limit of 95% CI of Observed Incidence Proportion
215	15%	32	10.5%	20.5%
245	18%	44	13.4%	23.4%
264	20%	52	15.3%	25.3%

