282	22%	62	17.3%	27.3%
306	25%	76	20.2%	30.2%

*Rounded down to the nearest whole number

A sample size of 270 is recommended to achieve 5% precision (half width). Considering a drop-out rate of 20%, 340 patients in each arm are needed.

To provide further justification about detecting potential increased risk given the calculated sample size above, the power calculation is presented in Table 4 below assuming 20% incidence proportion in the comparator arm and varied increased incidence proportions in the treatment arm with two-sided 0.05 alpha level using normal approximation. With 270 patients who complete the study in each arm, there is 84% power to detect an 11% risk increase.

Table 4: Power calculations to detect potential increased risk

Risk Increase	Expected Proportion for Comparator Arm	Expected Proportion for Treatment Arm	Completion Status	Sample Size in Each Arm	Power
9%	20%	29%	Completers Only	270	69%
10%	20%	30%	Completers Only	270	77%
11%	20%	31%	Completers Only	270	84%
12%	20%	32%	Completers Only	270	89%
9%	20%	29%	Completers + 30 Drop-outs	300	73%
10%	20%	30%	Completers + 30 Drop-outs	300	81%
11%	20%	31%	Completers + 30 Drop-outs	300	88%
12%	20%	32%	Completers + 30 Drop-outs	300	92%
9%	20%	29%	Completers + 60 Drop-outs	330	77%
10%	20%	30%	Completers + 60 Drop-outs	330	85%
11%	20%	31%	Completers + 60 Drop-outs	330	90%
12%	20%	32%	Completers + 60 Drop-outs	330	94%

Owing to the study design with 5-year enrollment and 5-year follow-up, patients will be followed between 5 to 10 years. A discontinued patient enrolled early and discontinued not soon after enrollment will be included in the analysis with possible long follow-up time. For example, the first enrolled patient discontinued at year 6 will have longer follow-up time than the last enrolled patient who has only 5-year

follow-up at maximum. Therefore, early discontinued patient may still contribute high-quality information with acceptable follow-up time to the analysis. Additional power analysis is provided in Table 4 assuming 270 completers +30 and +60 early discontinued patients being included in the analysis, and there is >80% power to detect a 10% risk increase.

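### Section 9.7 fixes a normal-approximation 95% CI for every person-time rate, with no exception for few or zero events, where its upper limit is too low or the interval fails

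*Protocol*

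**What the plan says.** Under the primary objective, section 9.7 of the protocol prescribes: "The rate per person-year exposure with a 95% CI will be constructed using asymptomatic normal approximation". The word *asymptomatic* is a slip for *asymptotic*. The sentence appears again under the exploratory objectives, followed by "This will be done for the following subgroups" and a list of four subgroup pairs, one of which is "patients who have received live/attenuated vaccine and patients who have not received live/attenuated vaccine". Between the two, under Events of Interest, the section adds: "Statistical analysis of malignancy and other events of interest will follow the same method as those for serious infections".

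The section does not say whether the approximation is on the raw or the log scale, which variance estimator is used, or whether a rate counts first events or all events. It offers no alternative for small or zero counts.

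The protocol gives no subgroup sizes. Section 7 makes enrolment of the special populations conditional: "If these patients are enrolled into the study, the safety of efgartigimod will be assessed in these patient populations". Table 2 in section 9.3 asks for severe renal impairment separately from moderate, although the list in 9.7 pools the two. On size and follow-up, section 9.5 states "A sample size of 340 patients in each of the two cohorts is proposed (680 patients in total"), based on 270 evaluable patients per cohort and 20% drop-out, and that "patients will be followed between 5 to 10 years".

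**The concern.** A normal-approximation interval for a Poisson rate works when the count is large. When the count is small, its standard error is estimated from that same small count: too few events by chance gives both a low estimate and a narrow interval. For a rare safety event the useful question is how high the rate could still be, and that is the end of the interval that fails.

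This is not a detail left to the SAP, because the protocol itself names the method and applies it to all rates. Estimating incidence rates is the study's stated research question and the analysis is mainly descriptive, so these intervals are a main output. The risk is false reassurance where data are thinnest: the populations listed as missing information in the risk management plan, and possibly malignancy.

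**Working it through.** **The protocol's own figures first.** Section 9.5 reproduces: Clopper-Pearson limits for 20% of 264 are 15.35% to 25.34% (stated 15.3% to 25.3%), and 270 / 0.8 = 337.5, or 338 (stated 340). The protocol states no coverage for the rate interval, so there is nothing further to reproduce.

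**Formulas.** Let x be the observed number of events, PY the person-years and μ the expected number of events.

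- Raw-scale normal interval: (x ± 1.96√x) / PY.
- Exact Poisson interval: lower χ²(0.025; 2x) / 2 / PY, upper χ²(0.975; 2x + 2) / 2 / PY.
- Coverage at μ: the sum of Poisson(μ) probabilities over all x whose interval contains μ.

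**Coverage by expected events.** The low values of μ are assumptions.

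| μ | Raw normal | True rate above upper limit | True rate below lower limit | Exact Poisson |
|---|---|---|---|---|
| 1 | 63.2% | 36.8% | 0.1% | 98.1% |
| 2 | 86.4% | 13.5% | 0.1% | 98.3% |
| 2.5 | 91.7% | 8.2% | 0.1% | 98.6% |
| 3 | 79.7% | 19.9% | 0.4% | 98.8% |
| 4 | 90.6% | 9.2% | 0.3% | 96.0% |
| 5 | 87.0% | 12.5% | 0.6% | 98.0% |
| 10 | 92.6% | 6.7% | 0.7% | 97.5% |
| 54 | 94.5% | 4.0% | 1.5% | 95.9% |

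Coverage is not monotone. On a fine grid between 1 and 5 it runs from 63.2% up to 94.7% at isolated values. Below 1 it is worse (39.3% at 0.5). On the log scale, coverage at 1, 2, 3, 4 and 5 expected events is 61%, 81%, 92%, 93% and 96%.

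**Individual intervals, in events.**

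- x = 0: raw 0 to 0; log scale undefined; exact 0 to 3.69. With 100 PY the exact upper limit is 3.7 per 100 PY; with 1350 PY it is 3.69 / 1350 = 0.27 per 100 PY.
- x = 3: raw 3 ± 1.96 × 1.73 = −0.4 to 6.4; exact 0.6 to 8.8.

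**Serious infection, full cohort.** 270 × 20% = 54 events; coverage 94.5%.

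**Serious infection, small subgroup.** With the same 20% and assumed sizes of 5, 10, 20 and 30 patients, the expected counts are 1, 2, 4 and 6, and coverage is 63%, 86%, 91% and 93%.

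**Malignancy, full cohort.** Taking 270 × 5 years = 1350 PY:

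- Section 7 gives neoplasms in 1 of 84 (1.2%) over 26 weeks, about 2.4 per 100 PY, and in 5.0% over a mean of 363 days, about 5.0 per 100 PY. These give about 32 to 68 events and about 95% coverage. They count any neoplasm, so they are an upper guide to the narrow malignancy definition in Table 2.
- Assumed rates of 1.0, 0.5, 0.2 and 0.1 per 100 PY give 13.5, 6.8, 2.7 and 1.4 events, and coverage of 94.7%, 90.0%, 93.1% and 74.0%.
- Five or fewer expected events requires 5 / 1350 = 0.37 per 100 PY or less, or much less counted exposure.

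**An illustration from the protocol.** Section 7 reports no serious infection in the 84 efgartigimod patients of the placebo-controlled study. Assuming 26 weeks each, that is about 42 PY. The raw interval would be 0 to 0; the exact upper limit is 3.69 / 42 = 8.8 per 100 PY. Section 9.5 later gives 6.2% over a mean of 1.7 years in the extension study, roughly 6.2 / 1.7 = 3.6 per 100 PY. The raw interval excludes that rate; the exact one includes it.

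**The case against.** The strongest reply is that the poor coverage depends on counts the protocol does not give. That stands: the 1 to 5 range is an assumption. A reader might infer that malignancy intervals will undercover as a matter of course. The documents do not support that, because the only related figures in the protocol point to near-nominal coverage in the full cohort.

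Second, the exploratory outcomes are all AEs and SAEs. AEs are frequent: section 7 reports treatment-emergent infections alone in 46.4% of treated patients in the placebo-controlled study. Overall AE rates will usually rest on enough events even in modest subgroups. This also stands, and it confines the problem to SAEs, individual terms and very small groups.

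Third, the scale is unstated. Negative limits and 0-to-0 intervals belong to the raw scale. A log-scale interval avoids both and does well at 5 events, but it is still poor at 1 or 2 and has no value at zero, so the gap remains on either reading.

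A reader might also infer that the prescribed interval treats repeated events in one patient as independent. The text does not say so: it names no variance estimator and does not say which events a rate counts. Nor is there a contradiction with the exact limits in section 9.5, which concern a binomial proportion used for planning.

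Finally, the logistic and Cox comparisons between cohorts do not use this interval. That is correct and limits the consequence to the descriptive intervals.

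**Conclusion.** The point holds in conditional form. The protocol prescribes one interval method for all person-time rates and makes no provision for the counts at which it fails. At the tabulated means from 1 to 5 expected events, raw-scale coverage is about 63% to 92%, touching 94.7% at some values between them, and the error is almost always an upper limit that is too low. At zero events the interval is 0 to 0 or undefined.

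This rests on assuming that some reported rates will have so few events. That is plausible for SAEs or single terms in subgroups such as live vaccine or severe renal impairment, for the year 4 interim report, and for malignancy if its rate is about 0.4 per 100 PY or lower at 1350 PY. It is not shown for malignancy at the protocol's own any-neoplasm rates, and it does not affect full-cohort serious infection or the model-based comparisons. The change is worth making because it is cheap and the failure is in the unsafe direction.

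**What to change.** In both places in section 9.7:

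- Replace the normal approximation with exact (chi-square) Poisson limits for rates based on first events, that is, patients with the event divided by person-time to first event.
- State that if a rate counts repeated events per patient, its interval will use a patient-clustered or negative-binomial variance.
- Correct *asymptomatic* to *asymptotic* wherever the term is kept.

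The reference from malignancy and other events of interest to the same method then carries the change without further editing.

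The cost is a sentence in two places and standard software, with no new data. Intervals for rare events become somewhat wider and slightly conservative (96% to 99% coverage at 1 to 5 expected events). At the size of the main serious-infection analysis little changes: for 54 events the limits are 39.6 to 68.4 by the raw normal method and 40.6 to 70.5 exactly.
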